The primary outcomes are consumer understanding and purchase intentions, each analyzed as repeated measures at the post level:

1. **Consumer understanding** will be measured by whether participants correctly identify the product featured in each post as UPF. Responses will be coded as correct if participants select "Yes" when asked whether they think the product featured in the post is UPF; "No" and "*I don't know*" will be coded as incorrect.
2. **Purchase intentions** will be measured for each social media post by asking participants how likely they would buy the product in the next week using a 1–5 Likert scale, with 5 indicating "*very likely*" (treated continuously).

Secondary Outcomes

The secondary outcomes are perceived healthfulness (analyzed as a repeated measure at the post level), and perceptions of control over healthy eating and policy support (both analyzed at the participant level as each participant answered these questions only once after viewing all posts):

1. **Perceived healthfulness** will be measured for each social media post by asking participants how healthy the product seems to them using a 1–5 Likert scale, with 5 indicating “*very healthy*” (treated continuously).
2. **Perceptions of control over healthy eating** will be measured by participants’ categorical responses to how an UPF warning label would make them feel. Response options will be coded as follows: “*More in control of making healthy eating decisions*” will be coded as 1, while “*Less in control of making healthy eating decisions*” and “*Neither less nor more in control of making healthy eating decisions*” will be coded as 0.
3. **Policy support for ultra-processed food warning labels** will be measured by asking participants, “Would you oppose or support a policy requiring these labels on social media advertisements for ultra-processed foods and beverages?” using a 1–5 Likert scale, with 5 indicating “*strongly support*” (treated continuously).

Statistical Methods

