- a. We will use the same model from 2b to evaluate the effects of UPF warning labels on perceived healthfulness. Perceived healthfulness will be regressed on trial arm (warning label vs. control), and we will estimate and report the average perceived healthfulness for each group, as well as the ADE.
- b. We will describe the percentage of participants (pooled across trial arms) who report increased control over healthy eating. Similarly, we will describe the percentage of participants who report supporting requiring UPF warnings. We will additionally describe these percentages stratified by age group (teens vs. young adults) and gender (male vs. female).

4. Exploratory Analysis:

- a. We will use chi-square tests to compare the distribution of UPF understanding categories (low/moderate/high) between trial arms. If the distributions do not differ significantly, we will proceed to test participants' understanding of the term "ultra-processed food" as a moderator in section 4b. This step is to make sure that being exposed to the warning labels does not influence their understanding of the term.
- b. We will examine whether participants' understanding of the term "ultra-processed food" moderates the effect of the label on consumer understanding, purchase intention, perceived healthfulness, perceptions of control over healthy eating, and policy support for UPF warning labels. Moderation will be tested by adding UPF understanding and its interaction with trial arm to the mixed models described in sections 2 and 3. If interactions are significant, we will report stratified effects.

5. Additional considerations and sensitivity analyses:

- a. If models fail to converge for the repeated measures (unlikely), we will test simpler covariance structures.
- b. For repeated measures, we will additionally add fixed effects for social media posts in the mixed models to adjust for any systematic differences across the social media posts.

- c. For consumer understanding (binary), we will conduct sensitivity analyses using Poisson GEE models with a log link (to estimate risk ratios for consumer understanding) and robust standard errors.

Sample Size Needs

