We plan to collect data from 1,000 participants. With 80% power and a two-sided alpha of 0.05, we can detect an effect size of approximately Cohen's $d = 0.18$ for non-repeated-measures outcomes. For repeated measures, assuming four repeated measures per participant, the minimal detectable d is approximately 0.13–0.16, assuming within-person correlation $\rho=0.4–0.7$. These represent small effect sizes, but ones that are meaningful at the population level.

Exclusions and Outliers

We will exclude participants who complete the survey implausibly quickly (defined as completing in less than one-third of the median completion time).

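### No overall label effect is planned for control over healthy eating or policy support, which does not fit item 4b or the sample size section

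*SAP*

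**What the plan says.** Under Secondary Outcomes, the SAP lists three outcomes. Perceived healthfulness is measured for each post. Control over healthy eating (binary: more in control versus less or neither) and policy support (1 to 5, treated as continuous) are each answered once, after all posts have been viewed. The policy item asks: "Would you oppose or support a policy requiring these labels on social media advertisements for ultra-processed foods and beverages". Under Study Protocol, labels appear on the posts according to trial arm, so both items follow the randomized exposure.

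Three places in the SAP then deal with these two outcomes:

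- **Statistical Methods, item 3b:** "We will describe the percentage of participants (pooled across trial arms) who report increased control over healthy eating". Policy support is to be described similarly, as a percentage. Both percentages are also given by age group and gender. Arm is not among the strata.
- **Statistical Methods, item 4b (exploratory):** asks whether participants' understanding of the term UPF "moderates the effect of the label on consumer understanding, purchase intention, perceived healthfulness, perceptions of control over healthy eating, and policy support". It does this by adding understanding and its interaction with arm to the mixed models of sections 2 and 3. It runs only if the chi-square test in 4a is not significant, and stratified effects are reported only if the interaction is significant.
- **Sample Size Needs:** "we can detect an effect size of approximately Cohen's $d = 0.18$ for non-repeated-measures outcomes".

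**The concern.** Item 3a, directly above 3b, regresses perceived healthfulness on arm and reports group averages and the difference. Item 3b does neither for the other two secondary outcomes, although they too are measured after randomization and exposure. Items 4b and Sample Size Needs read as if an arm comparison existed.

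Two things are at stake. First, if exposure shifts the answers, the pooled percentage is a mixture of two different response rates whose value depends on the allocation ratio, and the randomized information on these outcomes goes unused. Second, the pre-specification is open: 4b cannot be carried out as written for these outcomes, so someone will have to choose a base model later, and whether to report results by arm could be decided after the data are seen.

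**Working it through.** **1. The plan's own figure.** Inputs from Sample Size Needs: 1,000 participants, 80% power, two-sided alpha 0.05. The allocation ratio is not stated; 1:1 (500 per arm) is assumed.

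- Detectable d for two independent means = (z0.975 + z0.80) × √(2/n) = (1.960 + 0.842) × √(2/500) = 2.802 × 0.0632 = 0.177. The noncentral t distribution also gives 0.177. This rounds to the stated 0.18.
- Repeated measures, four per person: 0.177 × √((1 + 3ρ)/4) gives 0.131 at ρ = 0.4 and 0.156 at ρ = 0.7. This matches "the minimal detectable d is approximately 0.13–0.16".

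Both figures are right, and 0.18 is by construction a between-arm contrast.

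**2. Which planned analysis uses 0.18?** Consumer understanding, purchase intentions and perceived healthfulness are all repeated measures. That leaves control and policy support as the only primary or secondary outcomes asked once, and 3b plans no arm contrast for them. The 4a comparison of understanding categories between arms also uses one record per person, but it is an exploratory chi-square test on three categories, to which a Cohen's d does not directly apply.

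**3. Can 4b run as written?** It adds terms to models from sections 2 and 3. Section 2 models the primary outcomes, 3a models perceived healthfulness, and 3b contains no model. With one record per participant, a random intercept cannot be separated from residual error, so a random-intercept model does not suit these outcomes. Even with a workable base model, the arm coefficient in an interaction model is the label effect in the reference category of understanding, not the overall effect.

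**4. What pooling hides.** With label-arm share w, pooled rate = w × p(label) + (1 − w) × p(control). At w = 0.5, with assumed rates:

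| Control | Label | Pooled |
|---|---|---|
| 50% | 60% | 55% |
| 55% | 55% | 55% |
| 40% | 70% | 55% |

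The reported figure is the same in all three cases. These rates illustrate the point; the SAP gives none.

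**5. What a by-arm analysis would deliver at 500 per arm.**

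- *Control (binary), precision:* 95% CI half-width = 1.96 × √(2 × 0.5 × 0.5/500) = 6.2 points at rates near 50%.
- *Control, 80% power:* detectable differences of about 8.4, 8.8, 8.8, 8.5 and 7.8 points at assumed control rates of 30%, 40%, 50%, 60% and 70%. The 50% versus 60% case has about 89% power.
- *Policy support (1 to 5):* 0.177 × SD gives 0.18, 0.21 or 0.25 scale points at an assumed SD of 1.0, 1.2 or 1.4.
- *If speed exclusions left 450 per arm* (assumed 10% loss): d = 2.802 × √(2/450) = 0.187, and the detectable binary difference at 50% is about 9.3 points.

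**The case against.** The best defence is that pooling is deliberate. Item 3b states it outright for control. That item asks how a label would make respondents feel, which people in either arm can answer. The Introduction names only consumer understanding and purchase intentions as the outcomes on which the label's effect is assessed, and General Principles calls the study exploratory. Where the authors want an arm effect (2a, 2b, 3a), they specify a regression on arm. A descriptive target for two attitude items is legitimate in itself. That stands, but it does not explain 4b, which presupposes label effects on both outcomes, or the power statement. On either intention, some text has to change.

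Three stronger readings are tempting and are not supported:

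- *That the label's effect on these outcomes is never estimated.* Item 4b could yield label effects within strata of understanding. What is missing is an unconditional, overall effect.
- *That the outcomes are reported only as one pooled figure.* Age and gender strata are planned. The explicit pooling is also attached to control; for policy support it is inferred from the parallel wording and from the absence of arm among the strata.
- *That the pooled percentage is biased, or that control-arm answers lack a basis.* The SAP offers no evidence that exposure shifts the answers. Whether a label is displayed with these questions is a matter for the survey instrument, which is not shown.

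**Conclusion.** The point holds as an inconsistency in pre-specification. Item 3b plans pooled description, 4b builds on arm models that section 3 does not contain for these outcomes, and Sample Size Needs quotes a two-arm detectable effect that no planned analysis of a listed primary or secondary outcome uses. A reader might infer that the 0.18 is miscalculated; it is not.

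Two of the three secondary outcomes are affected, and the primary analyses are untouched. No error in a planned estimate is shown. The loss is a randomized contrast that the planned sample could estimate to within about 6 percentage points for control, or detect at d of about 0.18 for policy support. These sizes rest on 1:1 allocation, assumed response rates and SDs, and little loss to speed exclusions. The contradiction between the sections depends on none of these assumptions. The change should be made, but the trial does not stand or fall on it.

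**What to change.** **Preferred.** In 3b, keep the pooled percentages and add by-arm estimates with 95% CIs from linear models with one record per participant and robust standard errors:

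- a risk difference for feeling more in control;
- a mean difference on the 1 to 5 scale for policy support, since the SAP treats it as continuous.

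Label both as secondary and unadjusted for multiplicity. In 4b, replace the reference to mixed models with these participant-level models for the two outcomes. While editing 3b, state which responses on the 1 to 5 scale count as support, because the percentage is planned without a cut-off.

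**Alternative, less informative.** If pooling is truly intended, declare both outcomes descriptive, remove them from 4b and say which analysis the 0.18 refers to.

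**Cost.** The preferred option takes a few sentences of SAP text and no additional data. It adds two unadjusted secondary comparisons to a plan that already makes no multiplicity adjustment. The alternative adds no comparisons but gives up the randomized contrast on both outcomes.

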Complete Title: Online Randomized Experiment Evaluating Ultra-Processed Food Warning Labels on Social Media Posts Among Teens and Young Adults

Short Title: Effects of UPF Warning Labels on Social Media Among Teens and Young Adults

Protocol Date: August 25, 2025

NCT #: NCT07227519

Study Principal Investigators:

[name]

University of Tennessee Health Science Center

Email: [contact]

[name]

Stanford University

Email: [contact]

Introduction

The goal of the analyses described here is to use data collected through an online randomized experiment to examine teens' and young adults' responses to ultra-processed food (UPF) warning labels on social media posts. These analyses assess the effect of a highly visible UPF warning label displayed beneath social media posts, compared to a control condition with no label, on consumer understanding and purchase intentions. This analysis plan pre-specifies the analyses before collecting data and therefore serves as our ex-ante planned analysis.

Study Protocol

Participants will complete an online randomized experiment. After providing informed consent, they will be randomized to one of two trial arms: (1) UPF warning labels or (2) no-label control. Participants will view four social media posts (presented in random order; all feature UPF) based on real Instagram posts from leading food and beverage companies. Labels will be shown according to participants' assigned trial arm. Participants will then respond to survey questions assessing consumer understanding, purchase intentions, perceived healthfulness, perceptions of control over healthy eating, and policy support for ultra-processed food warning labels. At the end of the UPF survey, participants will also answer an open-ended question on their understanding of the term "ultra-processed food."

Statistical Considerations

General Principles

We will use a two-sided critical alpha of 0.05 for all statistical tests. All confidence intervals will be two-sided and set at the 95% level. Analyses will be conducted on an intent-to-treat basis and will not be adjusted for any covariates, given the randomized design. Missing data will be handled in linear mixed models through maximum likelihood estimation (assumes missing at random [MAR]). Given the exploratory nature of the study, we will not adjust p-values for multiple comparisons.

Primary Outcome

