1. We will describe participant characteristics by trial arm. We will use means and standard deviations to characterize continuous variables and frequencies and percentages to characterize categorical variables. For the open-ended question on the participants’ understanding of the term “ultra-processed” (UPF understanding) we will develop a codebook using a hybrid inductive-deductive approach, and two independent reviewers will categorize the responses into ‘low,’ ‘moderate,’ and ‘high’ understanding.
2. Analyses of the primary outcome:
 - a. We will evaluate the effects of UPF warning labels on consumer understanding using a linear probability mixed model with random intercepts to account for repeated measures within participants. Consumer understanding (binary indicator) will be regressed on trial arm (warning label vs. no-label control). We will report the marginal predicted probability of consumer understanding in each group, as well as the average differential effect (ADE), defined as the risk difference (i.e., the difference in predicted probability between the warning label group and the control group). We opted for a linear probability mixed model rather than a logistic mixed model because we are interested in estimating risk differences.
 - b. We will evaluate the effect of UPF warning labels on purchase intentions using linear mixed models with random intercepts to account for repeated measures within participants. Purchase intention will be regressed on trial arm, and we will estimate and report the average purchase intention for each group, as well as the ADE.

c. We will test whether the effects of UPF warning labels on the co-primary outcomes (consumer understanding and purchase intentions) differ by age group (teens vs. young adults) and gender (male vs. female). To test for moderation, we will regress each primary outcome on intervention assignment and include interaction terms between intervention assignment and each moderator, using separate mixed models. We will test the significance of the interaction terms and, if significant, report the marginal effects of the UPF warning labels at each level of the moderator.

3. Analyses of secondary outcomes:

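### Exploratory sections 4a–4b: a non-significant chi-square cannot show that the labels left UPF understanding unchanged, so it cannot clear this post-exposure item for use as a moderator

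*SAP*

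**What the plan says.** The Study Protocol section of the SAP places the item after the posts have been viewed and the other questions answered: "At the end of the UPF survey, participants will also answer an open-ended question on their understanding of the term". Under Statistical Methods, item 1, "two independent reviewers will categorize the responses into ‘low,’ ‘moderate,’ and ‘high’ understanding".

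Section 4a compares the three categories between arms by chi-square and sets a rule: "If the distributions do not differ significantly, we will proceed to test" the item as a moderator. The purpose given is "This step is to make sure that being exposed to the warning labels does not influence their understanding of the term".

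Section 4b covers five outcomes, including both co-primary outcomes. "Moderation will be tested by adding UPF understanding and its interaction with trial arm", and "If interactions are significant, we will report stratified effects".

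The SAP gives no power or equivalence margin for the chi-square test, no measure of understanding before exposure, and no caveat on using a variable measured after randomisation.

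**The concern.** A moderator should be a characteristic that the intervention cannot have altered. This one is recorded after the label arm has seen a label that names the very concept being asked about. The authors saw the problem, which is why 4a exists, but the safeguard fails for two separate reasons.

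- **Non-significance is not evidence of no influence.** A test that passes may simply have missed a real shift.
- **The test sees only category totals.** If the label moves some people up and others down, the totals can match while the people within each category differ between arms. A larger sample or an equivalence margin on the totals would not reveal this.

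If the label moves people between categories, comparing arms within a category is no longer a randomised comparison. The stratified label effects in 4b then mix the effect of the label with a difference in who is being compared, and could be misread as showing for whom labels work.

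**Working it through.** **Inputs.** From the SAP: 1,000 participants, two arms, two-sided alpha 0.05, three categories. Assumed, because the SAP does not give them: 1:1 allocation (500 per arm); control low/moderate/high shares of 33/33/33, 50/30/20, 40/40/20 or 60/30/10; and the outcome model in step 4.

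**1. The SAP's own figure.** Under Sample Size Needs, the detectable effect for non-repeated outcomes is d of about 0.18. It reproduces: (1.960 + 0.842) × √(2/500) = 0.177. The SAP states no corresponding figure for the chi-square in 4a.

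**2. Chance that 4a passes despite a real shift.** The test has 2 degrees of freedom and critical value 5.99. With control shares p, label-arm shares q and m = (p + q)/2, the non-centrality is λ = 500 × Σ[(p − m)² + (q − m)²]/m. The pass rate is the probability that a non-central chi-square (2 df, λ) falls below 5.99.

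Example: 40/40/20 becoming 35/40/25. The moderate share does not change, and m is 0.375 for low and 0.225 for high. So λ = 500 × (2 × 0.025²/0.375 + 2 × 0.025²/0.225) = 4.44, and the pass rate is 0.544. For 80% power λ must reach 9.63, that is w = √(9.63/1000) = 0.098.

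| Low-to-high shift | 33/33/33 | 50/30/20 | 40/40/20 | 60/30/10 |
|---|---|---|---|---|
| 3 points | 0.835 | 0.821 | 0.809 | 0.742 |
| 4 points | 0.735 | 0.712 | 0.691 | 0.582 |
| 5 points | 0.606 | 0.576 | 0.544 | 0.409 |
| 6 points | 0.460 | 0.429 | 0.390 | 0.255 |
| 8 points | 0.195 | 0.179 | 0.144 | 0.067 |
| 10 points | 0.051 | 0.049 | 0.032 | 0.011 |

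At 450 per arm (10% excluded, assumed) the ranges are 76–85% at 3 points, 46–64% at 5 and 10–24% at 8.

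**3. What a pass is compatible with.** The 95% CI half-width for a between-arm difference in one category share is 1.96 × √(2p(1 − p)/500): 3.7 points at p = 0.1, 5.0 at 0.2 and 6.2 at 0.5.

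**4. Effect on the strata.** Take 40/40/20, a true label effect of 0.20 SD in every category (no moderation), an outcome rising by b SD per category, and movers who keep their original outcome level.

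- *5 points low to high.* The label arm's high category holds 20 original points and 5 movers, each mover 2b lower. The high-stratum effect is 0.20 − (5/25) × 2b, which is 0.16, 0.08 and 0.00 at b = 0.1, 0.3 and 0.5.
- *3 points low to high.* 0.20 − (3/23) × 2b gives 0.17, 0.12 and 0.07.
- *5 points low to moderate.* The moderate-stratum effect is 0.20 − (5/45) × b, which is 0.19, 0.17 and 0.14.

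**5. False interactions.** Simulation under the same model: 3,000 runs per setting, 500 per arm, residual SD 1, 2-df interaction F test at 0.05, counting only runs in which 4a passed. Figures are for b = 0.1, 0.3 and 0.5; repeat simulations differ by up to about 3 percentage points.

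| Movement | False interaction |
|---|---|
| None | about 5% throughout |
| 5 points low to moderate | 5%, 5%, 7% |
| 5 points low to high | 6%, 11%, 20% |
| 5 points each way between low and high, totals equal (4a passes 95%) | 7%, 20%, 45% |

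The simulated stratum effects agree with the arithmetic in step 4.

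**The case against.** The strongest reply is about weight. Section 4 is labelled exploratory, the authors anticipated the problem, and the check has some force: it usually catches shifts of 8 points or more. The largest harm figures need unusual patterns. For 45% false interactions, a quarter of the high group (5 of 20 points) must fall two categories after seeing a warning label, with a 1.0 SD outcome gap between low and high. The 20% figure needs movers to skip the moderate category and the same gap. Movement between adjacent categories leaves the interaction test near its nominal level in most settings, and so did a small uniform upward shift of 0.10–0.15 SD in a separate simulation (about 5%). The model is also a single continuous outcome, whereas 4b includes a binary repeated outcome and four-post Likert outcomes.

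Much of this stands as a limit on size. The 20% and 45% figures are extreme cases, and the actual bias cannot be derived from the SAP. It does not rescue the inference. A 3-point shift, which passes 74–84% of the time, can still pull the high-stratum effect from 0.20 to between 0.17 and 0.07. Exploratory status excuses unadjusted p-values; it does not justify a pre-specified assurance that the test cannot supply.

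A further objection is that dropping the check would leave open when 4b is run. That is met by keeping the existing rule for when to proceed and changing only what may be concluded.

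**Conclusion.** The point holds. The SAP draws a wrong inference in writing: it takes a non-significant chi-square as proof that exposure did not alter understanding, then treats a post-exposure variable as a moderator. Under 1:1 allocation and the four assumed control distributions, a real 5-point low-to-high shift is missed 41–61% of the time. Movement that leaves the totals equal is essentially invisible to the test. The consequence for 4b ranges from negligible to a false interaction, depending on who moves and how strongly the outcome varies with understanding, neither of which the SAP fixes.

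The reach is limited to exploratory sections 4a–4b. The primary and secondary analyses in sections 2–3, including the age and gender moderation in 2c, do not depend on it. The text should be corrected before analysis, but the trial's main conclusions are not at risk.

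**What to change.** In 4a, delete the sentence giving the purpose of the step, and report the between-arm difference in each understanding category with its 95% CI as a result in its own right. The rule on when to proceed to 4b may stay as a rule of procedure, but a p-value of 0.05 or more should not be cited as support for a moderation claim.

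In 4b, present the results beside those intervals as a descriptive association with a variable measured after exposure, make no causal claim of moderation, and say plainly where the intervals show or allow a material shift.

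The cost is SAP wording, confidence intervals for a comparison already planned, and a weaker claim from an exploratory analysis. No new data and no change in sample size are needed.

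Optionally, and not as part of this fix, asking the item before the posts would give a true baseline moderator but risks priming participants. That trade-off is the sponsor's to make.

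### Does exploratory item 4b commit the analysts to an unidentifiable random-intercept model for the two outcomes that are asked only once?

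*SAP*

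**What the plan says.** In the SAP's Statistical Methods, item 4b asks whether a participant's grasp of the term UPF moderates the label effect on five outcomes. The last two listed are "perceptions of control over healthy eating, and policy support for UPF warning labels". One sentence gives the model for all five: "Moderation will be tested by adding UPF understanding and its interaction with trial arm to the mixed models described in sections 2 and 3". The reporting rule is "If interactions are significant, we will report stratified effects". Item 4b is reached only if the chi-square test in 4a shows no significant difference between arms in the understanding categories.

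The models it points back to are these:

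- **2a, consumer understanding:** "using a linear probability mixed model with random intercepts to account for repeated measures within participants", with the linear form chosen "because we are interested in estimating risk differences".
- **2b, purchase intentions:** a linear mixed model with a random intercept, given for the same purpose.
- **3a, perceived healthfulness:** "We will use the same model from 2b to evaluate the effects of UPF warning labels on perceived healthfulness".
- **3b, perceived control:** "We will describe the percentage of participants (pooled across trial arms) who report increased control over healthy eating".
- **3b, policy support:** "Similarly, we will describe the percentage of participants who report supporting requiring UPF warnings".

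The Secondary Outcomes section separates perceived healthfulness, a repeated measure per post, from the other two. Those two are asked once, after all the posts, and are to be handled at participant level. Control is coded 0/1. Policy support is a 1–5 score treated as continuous.

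**The concern.** Two of the five outcomes in 4b have no mixed model in sections 2 or 3. Item 3b gives only percentages, with no regression and no arm term, so there is nothing to which an interaction could be added. If the random-intercept form were carried over anyway, each participant would contribute one record and the model would have two variance parameters of which only the sum can be estimated. Software may then warn, fail, or print a wrong standard error.

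This could matter because 4b makes the reporting of stratified effects depend on the significance of the interaction. A standard error that is too small could put a spurious moderator into the report even when the point estimate is right. Leaving the model unnamed also leaves some choice open in a plan meant to be fixed before data collection.

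**Working it through.** **Inputs from the SAP.** 1,000 participants, two-sided alpha 0.05 and 80% power (Sample Size Needs); three understanding categories (Statistical Methods, item 1); one response per participant for control and policy support, and four posts for the repeated outcomes. *Assumed:* 500 per arm, since the SAP states no ratio; understanding in about equal thirds in the simulations.

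**1. The plan's own figures.** For non-repeated outcomes, the minimal detectable d = (1.960 + 0.842) × √(2/500) = 0.177, against the stated 0.18. For four repeated measures, multiply by √((1 + 3ρ)/4): 0.177 × √0.55 = 0.131 at ρ = 0.4, and 0.177 × √0.775 = 0.156 at ρ = 0.7, against the stated 0.13–0.16. The figures reproduce. They also show that the SAP treats the single-response outcomes as a separate class with no within-person correlation.

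**2. Is the random intercept identified?** With one record per person, Var(y) = τ² + σ², so only the sum can be estimated. Profiling the log-likelihood over the within-person correlation in simulated data (n = 1,000) gave:

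| ρ | 1 record per person | 4 records per person |
|---|---|---|
| 0.01 | −1423.5158 | −5625.3 |
| 0.25 | −1423.5158 | −5197.9 |
| 0.50 | −1423.5158 | −5079.2 |
| 0.75 | −1423.5158 | −5225.1 |
| 0.95 | −1423.5158 | −5917.6 |

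The profile is flat with one record and clearly peaked with four. A fitted model on single records split the variance 0.4827 / 0.4827 and warned that the Hessian was not positive definite. This part of the concern is correct.

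**3. Does that damage the interaction test?** With one record per person, V = (τ² + σ²)I. Then

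- β̂ = (X′V⁻¹X)⁻¹X′V⁻¹y = (X′X)⁻¹X′y, which is the ordinary regression estimate.
- Cov(β̂) = (τ² + σ²)(X′X)⁻¹, which depends only on the estimable sum.

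The model has six coefficients: intercept, arm, two for understanding and two for the interaction. Under REML the sum is estimated by RSS/(1,000 − 6), so the standard error equals that of ordinary regression. Under maximum likelihood the divisor is 1,000, so the ratio is √(994/1,000) = 0.997. Inference on the interaction is therefore identified although the variance split is not.

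**4. Where the wrong standard errors come from.** Simulations with no true interaction, using statsmodels 0.14.6:

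- In 400 datasets (200 per outcome type) the interaction coefficient equalled ordinary regression to within 1e-13. The Hessian warning appeared in 81%. The printed standard error was more than 1% too small in 46.5% (score) and 47.5% (binary). The joint 2-df test rejected in 40/400 (10.0%), against 19/400 (4.8%) with ordinary regression.
- A repeat with 1,000 datasets gave 74 against 30 rejections. Together that is 40 + 74 = 114 against 19 + 30 = 49 of 1,400. The ordinary-regression count in the repeat was low by chance: 40,000 further datasets gave 5.1%.
- In 60 datasets the printed standard error was more than 1% too small in 40%, with a Hessian warning in 47 of 60. The standard error from the *same fits'* total variance equalled ordinary regression to about 1e-14. Rejections were 6/60 with the printed standard error, 3/60 with the total-variance one and 3/60 with ordinary regression.
- In 50 further datasets per outcome, the total-variance test rejected exactly as often as ordinary regression (1/50 score, 2/50 binary), under both REML and maximum likelihood.

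The excess rejections arise from how this package converts a near-singular Hessian into standard errors. They are not a property of the model.

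**5. What an analyst would do.** Secondary Outcomes puts these two outcomes at participant level. The random intercept in 2a and 2b has a stated purpose, repeated measures, which is absent here. Removing it leaves a regression on arm, understanding and their interaction: linear for the 1–5 score and, following the risk-difference preference in 2a, linear probability for control.

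**The case for a change.** The strongest case for a change is that 4b, taken at its word, sends two outcomes to models that do not exist, and that a pre-specified plan should not depend on the analyst reading past its wording. The fallback in 5a does not help, because it covers only convergence failure for repeated measures. One package, used literally, rejects about twice as often as ordinary regression. The form of the analysis is also partly open: control could be modelled as linear probability, logistic or Poisson, and policy support is a score under Secondary Outcomes but a percentage in 3b. One sentence would settle all of this.

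Some of this stands. The cross-reference is loose, the random intercept is not identified for these outcomes, and neither model nor scale is named. The error-rate argument does not stand. It needs a literal reading that other parts of the SAP contradict, one particular package when the SAP names none, and disregard of a warning that appeared in most fits. The openness over scale is narrowed by the SAP's own outcome definitions and by its reason for linear models in 2a. The percentage in 3b is a descriptive summary and does not redefine the outcome. Adding a sentence would tidy the text, but it would not alter an estimate or a valid test.

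**Conclusion.** The observation about the text is correct, but no change to the plan follows. One collective phrase covers five outcomes when it fits three, and the rest of the SAP tells the analyst what to do with the other two. The effect on results is nil for the interaction estimate. For its model-implied standard error it is nil under REML and 0.3% under maximum likelihood (ratio 0.997). The roughly doubled rejection rate seen in simulation belongs to one package's printed output and is not the Type I error of the plan.

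The reach is also small: two of five outcomes, in an analysis labelled exploratory and run only if 4a is non-significant. No primary analysis, section 3 analysis or sample-size figure is touched.

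This rests on 1:1 allocation and roughly equal understanding categories for the numerical illustrations. The equality of the estimates does not depend on either, nor does REML's agreement on the standard error; the 0.997 depends only on 1,000 participants and six coefficients. It also rests on the analyst following the participant-level statement in Secondary Outcomes, or heeding the software warning if not.
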